- 2. To determine pre- and post-intervention knowledge, attitudes, beliefs and behaviours (KABB) of target adults, pharmacists, physicians, and vaccine providing nurses.

Secondary Objectives:

- 1. To assess the impact of various funding models on vaccination coverage.
- 2. To evaluate a pharmacy-based strategy for recruiting participants for a patient-reported active adverse event following immunization surveillance system.

Primary Hypothesis:

 Vaccine coverage with all studied vaccines will increase significantly after implementation of the bundled pharmacist-delivery strategy. A significant increase will be defined as an increase of ≥10% vaccine coverage from pre-program levels.

Secondary Hypotheses:

1. The cost of a vaccine is a key factor in an individuals' decision-making

ROMEO File #: 1021559

with respect to vaccination. It is expected that vaccinations provided at no or minimal charge will have higher uptake than those that require more financial resources to obtain.

2. We hypothesize knowledge about the vaccines studied, high dose TIV, meningococcal B vaccine, meningococcal ACWY vaccine, and Tdap, is low among the general public, but high among practitioners. We hypothesize we will find a high level of support among both the public and health care providers for pharmacists to provide vaccines measured in our study. Knowledge and support amongst both providers and the public will increase after implementation of the program.

Study Methodology

design

This will be a two-year demonstration program implementation and evaluation project in two Canadian provinces, New Brunswick and Nova Scotia. One community in each province will be allocated to implementation strategies specifically designed for each of the target vaccines. One community in each province will serve as the non-intervention control arm where pharmacist immunization practice will continue unchanged.

Inclusion criteria for the selection of the four communities are a stable population, service by a regional hospital and community pharmacies, and lack of substantial health care spill-over to adjacent communities. Spill over is defined as a pattern of health-care utilization where patients regularly receive care at different regional health centres. Communities will be geographically separated to minimize potential spill over.

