2.2 Secondary Objectives

- 1. To assess the impact of various funding models on vaccination coverage.
- 2. To evaluate a pharmacy-based strategy for recruiting participants for a patient-reported active adverse event following immunization surveillance system.

2.3 Primary Hypothesis:

 Vaccine coverage with all studied vaccines (high dose TIV, meningococcal B vaccine, meningococcal ACWY vaccine, Tdap, herpes zoster vaccine, and travel health vaccines) will increase significantly after implementation of the bundled pharmacist-delivery strategy. A significant increase will be defined as an increase of ≥10% vaccine coverage from preintervention levels.

2.4 Secondary Hypotheses:

- 1. The cost of a vaccine is a key factor in the individual's decision to be vaccinated. It is expected that vaccinations provided at no or minimal charge will have higher uptake than those that require more financial resources to obtain.
- 2. Knowledge about the vaccines studied is low among the general public, but higher among practitioners. There is a high level of support among both the public and health care providers for pharmacists as immunizers. Knowledge and support amongst both providers and the public will increase after implementation of the program.

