3 STUDY DESIGN

3.1 Vaccine Coverage

There are numerous barriers that impede an individual from becoming vaccinated. A successful intervention should incorporate a multi-faceted approach to improve vaccine uptake. By combining, or bundling different communication strategies, financial incentives and promoting awareness about vaccines and who can administer them, this study seeks study seeks to improve uptake in vaccines with low coverage rates.

ROMEO File #: 1021559

To assess the effectiveness of bundled pharmacist-delivery strategy and to assess the impact of various funding models on vaccination coverage, a demonstration program implementation and evaluation project will be conducted in two New Brunswick and two Nova Scotia communities. One community in each province will serve as an intervention community in which implementation strategies specifically designed for each of the target vaccines will be used. One of the communities in each province will serve as the non-intervention control arm where immunization practice will continue unchanged.

It is hypothesized that vaccine coverage will increase significantly, defined as an increase of $\geq 10\%$ vaccine coverage from pre-program levels, after implementation of the pharmacist-delivery strategy. As public funding of vaccination is a key factor in individuals' decision-making with respect to vaccination, it is also expected that vaccinations provided at no or minimal charge will have higher uptake than those that require more financial resources to obtain.

All pharmacies in the intervention and control communities have been identified using data from Pharmacy Association of Nova Scotia and the New Brunswick Pharmacists' Association. Pharmacies interested in being involved with this research will serve on an advisory board with investigators for logistical and organizational purposes. Pharmacists employed at participating pharmacies will act as non-academic members of the research team who will deliver the targeted vaccines. All pharmacists receive training and certification in vaccine administration through provincial regulatory authorities. Members of the research team will provide additional support to pharmacists involved in the study to reinforce best practice strategies. Pharmacists in intervention communities will provide vaccines through bundling of different communication strategies and payment mechanisms depending on the vaccine.

Pharmacist Intervention Strategies:

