- 1. *Communication Strategies* Pharmacists and pharmacy staff in intervention communities will use various public communication strategies, including:
 - a. targeted mail outs and/or phone calls by pharmacies to individuals in their databases based on risk factors for contracting and/or transmitting vaccine-preventable disease (e.g., immunosuppressant medications, recent birth in family)
 - b. timed marketing linked to other vaccine clinics (e.g., influenza clinics) and awareness campaigns (e.g., back-to-school advertising)
- 2. *Payment mechanisms* Intervention communities will provide vaccine through the following payment mechanisms, based on the study vaccine:
 - a. universal vaccination with "publicly funded" vaccine (vaccine provided to individual without charge (i.e. Tdap vaccine))
 - vaccination using a co-pay model (individuals receive vaccine at no cost after paying a designated co-pay fee comprised of the pharmacy dispensing fee and any administration fee charged by the pharmacist immunizers (i.e. high-dose TIV); and
 - c. vaccination using the current private market model where vaccine would be purchased either by the recipient or through insurance (standard of care control arm, (i.e. Meningococcal serogroup B, Meningococcal serogroup ACWY and highdose TIV influenza, herpes zoster, and travel health vaccines).

The non-intervention control arm will be the current model wherein a patient specifically requests a vaccination or the pharmacist offers this option while the patient is in the pharmacy. This non-intervention arm will be compared to the intervention arm.

Inclusion criteria

Inclusion criteria for the selection of the four communities include population size (approximately 30,000 adults >18 years of age), stable population, service by a centralized regional hospital and local community hospitals, availability of community pharmacies, interest and availability of community pharmacists (sufficient numbers of pharmacists qualified to provide vaccinations), and lack of substantial health care spill over to adjacent communities. Spill over is defined as a pattern of health-care utilization where patients regularly receive care at different regional health centres. Communities will be geographically separated to minimize potential spill over.

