Based on this inclusion criteria, four communities were selected. Intervention communities in which the communication and payment strategies will be implemented are: Saint John, New Brunswick and New Glasgow/Pictou/Antigonish, Nova Scotia area, which include the smaller towns of Stellarton and Westville, Nova Scotia. Control communities where pharmacy delivered immunizations will be offered under their current model are: Moncton, New Brunswick and Kentville/New Minas/Wolfville, Nova Scotia, which include the smaller towns of Canning and Coldbrook, Nova Scotia. Intervention and control communities will be compared to one another to assess the effectiveness of the bundled strategies.

Payment mechanisms will be applied in intervention communities, excluding no client from this strategy. Communication strategies will be targeted based on the type of vaccine a client is eligible to receive. Pharmacists will contact clients over the age of 65 by phone or mail out to recommend high-dose TIV and contact clients who are 50 and older to recommend herpes zoster. Clients who are immunosuppressed may also receive phone calls/mail outs for vaccines against meningococcal disease. Individual eligibility will also be assessed by pharmacists during consultations. Through client's interaction to fill prescriptions, pharmacists have regular contact with high-risk individuals and are able to proactively and systematically review patients' medical histories and medications to remind them of the benefits of specific vaccinations. They can also implement awareness campaigns during travel season and school breaks to target clients who may be travelling to high-risk areas and should consider getting vaccinated to protect themselves against travel-related illnesses, such as Hepatitis A and Typhoid Fever.

Measurement of vaccine coverage

Vaccine coverage rates will be measured using the following:

- **1.** pharmacy database analysis,
- 2. public health vaccine reports by physicians,
- 3. number of vaccine doses delivered to pharmacies in all four regions, and
- 4. public survey within the study communities to determine immunization status.

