6 OUTCOME MEASURES AND STATISTICAL METHODS

6.1 Outcomes/analysis plan/sample size/statistics

6.1.1 Primary Outcomes

- 1. Population specific vaccine coverage before and after bundled pharmacist-delivery intervention.
- 2. Proportion of population in intervention districts whose supplementary health benefit plans cover studied vaccines.
- 3. Public KABB about vaccine preventable diseases and related vaccines before and after program implementation interventions.
- 4. Public willingness to pay and co-pay for studied vaccines.
- 5. Health care KABB regarding pharmacist- delivered vaccine programs.
- 6. Public and health care provider satisfaction with various models of vaccine program delivery.

ROMEO File #: 1021559

Proportions of influenza vaccine recipients who register for CANVAS and who complete the online AEFI survey in intervention versus control communities.

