determined by physician billing data and public health provision of vaccine to physicians relative to the Statistics Canada population age specific census data for that community. A study-specific system of reciprocal notification forms for family doctors will be implemented that is similar to that used for publicly funded routine vaccines. A third estimate of vaccine coverage will be vaccine doses distributed in the participating communities (obtained from the manufacturer) relative to the eligible population based on Statistics Canada census data (2011 and 2016 when available). The fourth estimate of vaccine coverage will be derived from the pre- and postprogram public survey. Binomial point estimates and confidence intervals will be made for vaccine coverage rate within site, and coverage will be compared between and among sites using confidence intervals for the difference of binomial proportions, Fisher's exact tests, and logistic regression. Using a margin of superiority of 10%, when comparing two coverage proportions within site or between sites, a sample size of 298 per group gives 80% power to conclude in favor of superiority when the true difference in proportions is at least 20%, and a sample size of 1209 per group provides 80% power when the true difference in proportions is at least 15%, assuming independent responses. However, it is anticipated that there will be dependence within the family unit regarding the decision to be vaccinated, in which case the precision on the binomial point estimate, and thereby, the required sample size, depends on the size of the family unit and the intraclass correlation. Assuming the family unit to consist of two adults, and under the worst-case scenario in which the decision on vaccination is fully concordant for the two family members, the required sample size per group to detect a specified difference is doubled, to 596 (2418) when the true difference is at least 20% (15%). Estimates of the intraclass correlation will be calculated using data from pharmacy databases and from the public survey portion of the study, and these will be used to adjust confidence intervals and test statistics to accommodate within family dependence (Donner, Brikett, & Buck, 1981).

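### The primary 10% rise in coverage is measured only against pre-program levels and is not tied to the control comparison, so a trend shared with the control communities counts toward it

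*Combined protocol and SAP*

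**What the plan says.** The success criterion is before-after throughout. The primary hypothesis in section 2.3 reads "A significant increase will be defined as an increase of ≥10% vaccine coverage from preintervention levels". The synopsis has "A significant increase will be defined as an increase of ≥10% vaccine coverage from pre-program levels", and section 3.1 opens its version with "It is hypothesized that vaccine coverage will increase significantly" and the same threshold. The first item in section 6.1.1 is "Population specific vaccine coverage before and after bundled pharmacist-delivery intervention". None of these names the control communities.

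The controls come in elsewhere. Section 3.1 says of the control arm "This non-intervention arm will be compared to the intervention arm" and, more pointedly, "Intervention and control communities will be compared to one another to assess the effectiveness of the bundled strategies". The communities were chosen, not randomised: "Based on this inclusion criteria, four communities were selected".

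The one statistical statement that could join the two is in section 6.2, item 3: "Using a margin of superiority of 10%, when comparing two coverage proportions within site or between sites". It gives 298 per group for a true difference of 20% and 1209 for 15%, each at 80% power, doubled to 596 and 2418 for full concordance within two-adult households. The synopsis carries the 596. Logistic regression is listed as a method without its terms.

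**The concern.** The first primary objective is the effectiveness of the bundle. A before-after rise contains both the effect of the bundle and whatever would have happened anyway over the two program years. The control communities exist to separate these, but the criterion does not use them.

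The section 6.2 margin does not settle the matter, because its two options have different flaws. The within-site comparison keeps shared trend. The between-site comparison removes shared trend but keeps baseline differences between selected communities. Neither is named primary, and a difference in change, which addresses both, is neither specified nor powered.

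For a given vaccine the 10% rule and the controlled comparison can therefore disagree, and the visible text does not say which governs. The synopsis says the results will go to public health to inform funding strategies, so attribution matters.

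**Working it through.** **Inputs.** From section 6.2: a 10% margin, 298 and 1209 per group, 80% power. From section 1.5: coverage rose 10.7% in US states where pharmacists could vaccinate and 3.5% where they could not, 1995 to 1999. From section 8.7: a two-year program. My assumptions: 10% means percentage points; responses are independent; baselines p0 are 5%, 10%, 20% and 40%; a cell is one arm in one period. The 3.5-point trend covers four years in another country, so I also use half of it (1.75) and zero.

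**Reproducing the plan.** n = [p1(1−p1) + p2(1−p2)](zα + zβ)² / (d − 0.10)², with rates centred on 0.5 and one-sided 0.05, so (1.645 + 0.842)² = 6.183.
- d = 0.20: 0.48 × 6.183 / 0.01 = 296.8, so 297 (stated 298).
- d = 0.15: 0.48875 × 6.183 / 0.0025 = 1208.7, so 1209 (stated 1209).

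Two-sided 0.05 gives 377 and 1535. One-sided 0.05 is thus inferred; the plan does not state it for coverage. The stated sizes belong to a contrast of two proportions.

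**The cited example.** 10.7 meets a rule of at least 10. Net of control it is 10.7 − 3.5 = 7.2, so 3.5/10.7 = 33% of the rise is background.

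**Chance of meeting the threshold for a true gain g and trend t.** With v(p) = p(1−p) and n = 298:
- before-after SE = √{[v(p0) + v(p0+t+g)]/n}
- net-change SE = √{[2v(p0) + v(p0+t) + v(p0+t+g)]/n}
- point rule: Φ((effect − 0.10)/SE)
- margin test: Φ((effect − 0.10)/SE − 1.645)

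Example with p0 = 0.05, t = 0.035, g = 0.072. Before-after: SE = √(0.17985/298) = 0.0246 and Φ(0.007/0.0246) = 0.61. Net: SE = √(0.30513/298) = 0.0320 and Φ(−0.028/0.0320) = 0.19.

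Point rule, g = 7.2 points, baselines 5% to 40%:

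| Trend | Before-after | Net change |
|---|---|---|
| 3.5 | 61% to 57% | 19% to 31% |
| 1.75 | 33% to 40% | 18% to 31% |
| 0 | 11% to 24% | 17% to 31% |

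Under the margin test at a 3.5-point trend, the figures are 9% to 7% before-after against 0.6% to 1.6% net.

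With no true effect (g = 0), the before-after point rule is met in 0.1% to 5% of cases at a 3.5-point trend and in 50% at a 10-point trend.

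**Power for the net change.** With flat controls the variance is [3v(p0) + v(p0+g)]/n and power is Φ((g − 0.10)/SE − 1.645). Example with p0 = 0.40, g = 0.20: SE = √(0.96/298) = 0.0568 and Φ(1.762 − 1.645) = 0.55.

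| Net gain, 298 independent per cell | 5% | 10% | 20% | 40% |
|---|---|---|---|---|
| 20 points | 91% | 80% | 65% | 55% |
| 15 points | 47% | 36% | 27% | 22% |

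Under the plan's full household concordance, 298 independent responses require 596 respondents per cell. For the 20-point gain the variance is 1.4, 1.6, 1.8 and 2.0 times that of the two-group contrast at the four baselines.

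**The case against.** The strongest reply is that the controlled comparison is neither absent nor unpowered. Section 3.1 promises it, and section 6.2 gives a margin, power and sample sizes that cover a between-site contrast, which removes shared trend if made in the post period. That stands: a reader might infer that the control comparison has no power figure, and the documents do not support this. Only the difference in change lacks one. Nor do they exclude a period-by-arm term in the logistic regression; they leave it unspecified.

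The illustration can also mislead. A 3.5-point trend plus a 7.2-point gain lands just above 10, so passing more than half the time is built in. A reader might infer that trend alone would often produce success, or that the net rule is always harder to meet. Neither follows. A small trend with no effect rarely passes. At zero trend the net rule passes a 7.2-point gain more often than the before-after rule, because its variance is larger. Section 1.2 says adult influenza increases have stagnated, so zero is plausible for that vaccine. The figures are per vaccine, and since the hypothesis covers all studied vaccines, joint success is rarer.

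Moving the threshold to the net change does set a stricter target when coverage is rising, and it brings an equal-trends assumption. These are costs to state. They do not justify a criterion for effectiveness that omits the control arm. Appendices A-E might contain the missing link and could not be checked.

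**Conclusion.** The point holds for the visible text and should be fixed. The primary criterion credits shared trend to the bundle, and nothing ties the 10% to the comparison that is meant to show effectiveness. This is more than missing detail, because the before-after rule is stated repeatedly.

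Its size is uncertain, since the documents give no trend for these communities. Under the working's assumptions, for a true gain below the threshold, the before-after point rule overstates success clearly at a 3.5-point trend, modestly at 1.75, and not at all at zero. Under the section 6.2 margin test the absolute chances are below 10% even at 3.5 points. A trend near 10 points would make the point rule a coin toss with no effect at all; a trend of that size is an assumption. If 10% were meant as relative, a vaccine at 5% coverage would need only 5.5%, and a very small shared trend would suffice.

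**What to change.** In the synopsis and sections 2.3, 3.1 and 6.2, define the primary effect for each vaccine as the pre-to-post change in the intervention community minus that in its same-province control, in percentage points, and apply the 10-point threshold to it. Estimate it with a period-by-arm contrast, province as a factor and the family-correlation adjustment already planned. Use sources with a pre-period measure, such as the public survey run before and after in all four communities. Report each province pair, and keep the before-after rise as a descriptive result.

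Restate power for this contrast with alpha, sidedness and cell size. Section 6.2 sizes the survey at 400 without saying whether that is per community or in total. For a 20-point net gain with independent responses, 400 in total per round (200 per cell) gives 79%, 65%, 51% and 42% at the four baselines; 400 per community (800 per cell) gives 99.9%, 99%, 95% and 89%.

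State two limitations: the contrast assumes equal trends within each province pair, which a single pre-period survey cannot check; and with two communities per arm, between-community variation is not captured, however many people respond.

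The cost is wording, one specified contrast and less favourable stated power, given the larger variance. No added enrolment is asked for, but without it the lower power must be accepted.

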1.2 Recommended and Funded Vaccines

Tdap and influenza vaccines are recommended and funded for adults in most provinces; however, uptake of these vaccines remains low according to the Public Health Agency of Canada (PHAC). Increases in influenza vaccination rates amongst adults have stagnated and Tdap coverage amongst adults is estimated to be well under 10% (Public Health Agency of Canada, 2015).

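### The hypothesis sections define a significant rise in coverage by size alone (at least 10%), while Section 6.2 sizes the study on superiority beyond a 10-point margin; the plan never links the two or states which decides

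*Combined protocol and SAP*

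**What the plan says.** Three places define success by size.

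- Section 2.3 (Primary Hypothesis): "A significant increase will be defined as an increase of ≥10% vaccine coverage from preintervention levels".
- Synopsis, Primary Hypothesis: "A significant increase will be defined as an increase of ≥10% vaccine coverage from pre-program levels".
- Section 3.1: "It is hypothesized that vaccine coverage will increase significantly, defined as an increase of" at least 10%, again measured from pre-program levels.

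Section 6.2, item 3 (vaccine coverage), uses the same figure differently. Its sample-size sentence opens "Using a margin of superiority of 10%, when comparing two coverage proportions within site or between sites". It then says that 298 per group "gives 80% power to conclude in favor of superiority when the true difference in proportions is at least 20" percent, and that "a sample size of 1209 per group provides 80% power when the true difference in proportions is at least 15" percent. Both sizes are doubled, to 596 and 2418, for a worst case of fully concordant two-adult families.

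The preceding analysis text in 6.2 lists confidence intervals for a difference of proportions, Fisher's exact tests and logistic regression, without saying which result settles the hypothesis. No alpha or sidedness is given for coverage; the 0.05 level appears only under the KABB surveys.

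**The concern.** A definition by size alone has no error control. A margin test requires evidence that the difference exceeds 10 points. The two can give different answers on the same data, and the plan does not say which governs primary objective 1. An analyst could settle the matter after seeing the results, and the synopsis says those results will go to public health to inform funding decisions.

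Two further points are left open. The scale of the 10% is not plainly stated in the hypothesis sections, whereas 6.2 works with an absolute difference in proportions. The comparison also differs: before versus after in 2.3, within or between sites in 6.2.

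**Working it through.** **Inputs from the plan (6.2):** margin 10 points; true difference 20 or 15 points; power 80%; 298 or 1209 per group. **Assumed, because not stated for coverage:** one-sided 5%, and proportions symmetric about 50% (40% v 60%; 42.5% v 57.5%).

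**1. Reproduce the plan's sample sizes.**

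n = [p1(1−p1) + p2(1−p2)] × (z_alpha + z_power)² / (d − 0.10)², with (1.6449 + 0.8416)² = 6.1826.

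- d = 0.20: 0.48 × 6.1826 / 0.10² = 296.8, so 297 (plan: 298).
- d = 0.15: 0.48875 × 6.1826 / 0.05² = 1208.7, so 1209 (plan: 1209).

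Two-sided 5% would give 377 and 1535. A test against zero difference would need only 97 and 174 (two-sided 5%). The stated sizes therefore rest on a genuine 10-point margin test.

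**2. Smallest observed rise that shows superiority.** Find the smallest d with d − 1.645 × √{[p1(1−p1) + p2(1−p2)]/n} > 0.10, where p2 = p1 + d.

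| n per group | Assumed baseline 40% | Assumed baseline 5% |
|---|---|---|
| 298 | 16.6 points | 14.3 points |
| 1209 | 13.3 points | 12.1 points |

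Check at 298 and 40%: d = 0.1664 gives SE = √[(0.2400 + 0.2456)/298] = 0.0404, and 0.10 + 1.645 × 0.0404 = 0.166. With a two-sided 95% interval the 298 row becomes 17.9 and 15.2. The 5% column is shown because Section 1.2 says "Tdap coverage amongst adults is estimated to be well under 10" percent. At 596 per group with a design effect of 2, the effective size is again 298 and the thresholds are unchanged.

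With 30,000 per group treated as independent (Section 3.1 puts each community at about 30,000 adults), the threshold is 10.4 to 10.8 points across both baselines and both one-sided and two-sided 95% limits.

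**3. One data set, two answers.** 119/298 (39.9%) before and 155/298 (52.0%) after is a rise of 12.1 points, with SE = √[(0.2399 + 0.2496)/298] = 0.0405.

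- Size definition: 12.1 is at least 10, so it is met.
- Margin test: 12.1 − 1.645 × 4.05 = 5.4 points, so superiority beyond 10 is not shown (two-sided 95% interval 4.1 to 20.0).
- Fisher's exact test, as usually run against zero difference: p = 0.004.

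**4. Chance of meeting each criterion** (298 per group, 40% baseline, normal approximation). Size alone: Φ[(t − 0.10)/SE]. Margin test: Φ[(t − 0.10)/SE − 1.645].

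| True rise t | Observed rise at least 10 | Lower limit above 10 |
|---|---|---|
| 10 points | 50% | 5% |
| 12 points | 69% | 12% |
| 15 points | 89% | 34% |
| 20 points | 99% | 80% |

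The 5% in the first row is the intended error rate of a margin test at its boundary, not a fault in 6.2.

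**The case against.** A reader might infer that the plan contains two decision rules that are proven to contradict each other. The documents do not go that far. None of the three definitions says that the rise is the observed one. They stand as hypotheses, and a hypothesis about true coverage with Section 6.2 supplying its test is an ordinary structure that would remove the conflict. The margin, for its part, appears only in the sample-size sentence and is not declared as a pass/fail rule. This objection limits the claim but does not dispose of it: the sentences define significance by size, and nothing in the text makes the link.

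A reader might also infer that 10% is relative, so that Tdap could succeed on a trivial change (10% of an assumed 8% baseline is 0.8 points). The wording speaks of 10% vaccine coverage, which points more naturally to percentage points, as does the difference in proportions in 6.2. The relative reading is possible but weak, and supports only a request to state the scale. Section 3.1 refers vaccine-specific outcomes to the appendices, which are removed from the public copy and may hold more detail on this.

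The size of the gap depends on the data source. Three of the four coverage estimates use pharmacy databases or census denominators. With counts near 30,000 treated as independent, the two criteria nearly coincide. That holds against a single headline figure, but 6.2 also uses the public survey, expects dependence within families, and plans on 298 to 2418 per group.

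**Conclusion.** The point stands as an unsettled success criterion for the primary coverage hypothesis. The definition in the synopsis, 2.3 and 3.1 has no error control and differs from the criterion on which 6.2 sizes the comparison; no text reconciles them. The sample sizes themselves are not wrong.

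At the planned 298 to 1209 per group, the zone in which a rise meets 2.3 without showing superiority runs from 10 points up to between 12.1 and 16.6 points, given one-sided 5% and assumed baselines of 5% to 40%. It shrinks to under 1 point for independent counts near 30,000. For the same comparison and estimate on the absolute scale, disagreement runs one way: a lower limit above 10 implies an estimate above 10, but not the reverse. The practical risk is therefore of calling a rise significant when superiority has not been shown.

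**What to change.** State one rule in the synopsis, 2.3, 3.1 and 6.2: an increase is concluded when the lower confidence limit for the absolute difference in coverage, adjusted for within-family dependence as 6.2 already plans, exceeds 10 percentage points. With it:

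- give the confidence level and sidedness (one-sided 95% matches the stated sample sizes);
- name the comparison (within site or between sites) and which of the four coverage estimates the rule applies to;
- replace 10% by 10 percentage points throughout;
- report a rise of 10 points or more whose interval includes 10 as observed but not established.

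The cost is wording in four places, plus a decision on the comparison and the estimate. The stated sample sizes need not change. The downside is that the criterion becomes visibly stricter than 2.3 now suggests.
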